Research question and objectives	 The primary objectives of this study are: To describe the risk of ischemic stroke (IS)/ systemic embolism (SE) and intracranial hemorrhage (ICH) in patients with non-valvular atrial fibrillation (NVAF) and renal impairment initiating treatment with individual NOACs (rivaroxaban, apixaban, edoxaban) compared to phenprocoumon The secondary objectives of this study are: To describe the risk of ischemic stroke (IS)/ systemic embolism (SE) and intracranial hemorrhage (ICH) in patients with non-valvular atrial fibrillation (NVAF) initiating treatment with individual NOACs (rivaroxaban, apixaban, edoxaban) compared to phenproceet atrial fibrillation (NVAF) initiating treatment with individual NOACs (rivaroxaban, apixaban, edoxaban) compared to phenproceet atrial fibrillation (NVAF) initiating treatment with individual NOACs (rivaroxaban, apixaban, edoxaban) compared to phenproceet atrial fibrillation (NVAF) initiating treatment with individual NOACs (rivaroxaban, apixaban, edoxaban) compared to phenproceet atrial fibrillation (NVAF) initiating treatment with individual NOACs (rivaroxaban, apixaban, edoxaban) compared to phenproceet atrial fibrillation (NVAF) initiating treatment with individual NOACs (rivaroxaban, apixaban, edoxaban) compared to phenproceet atrial fibrillation (NVAF)

	phenprocoumon			
	 To describe the risk of IS, SE, kidney failure, acute kidney injury (AKI), fatal bleeding, recurrent hospitalization, recurrent IS/SE, severe IS as well as to describe treatment persistence in patients with NVAF (overall population as well as in specific subpopulations of interest) initiating treatment with individual NOACs (rivaroxaban, apixaban, edoxaban) compared to phenprocoumon 			
	Other objectives of this study are:			
	• To describe the risk of IS/ SE, severe IS, fatal bleeding and ICH as combined effectiveness outcome in patients with NVAF (overall population as well as in specific subpopulations of interest) initiating treatment with reduced dose of individual NOACs (rivaroxaban, apixaban, edoxaban) compared to standard dose in a subpopulation of patients without renal impairment			
Study design	Non-interventional cohort study based between January 2012 and December 2017. The enrollment period will be from 01 January 2013 to 30 June 2017. Data from 1 July to 31 December 2017 will be considered as follow-up only to allow a follow-up of at least 6 months.			

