8.3 Other objectives

Other objectives of this study are:

- To describe the risk of IS/ SE as combined effectiveness outcome in patients with NVAF (overall population as well as patients with renal impairment) initiating treatment with reduced dose of individual NOACs (rivaroxaban, apixaban, edoxaban) compared to standard dose in a subpopulation of patients without renal impairment
- To describe the risk of severe IS in patients with NVAF (overall population as well as patients with renal impairment) initiating treatment with reduced dose of individual NOACs (rivaroxaban, apixaban, edoxaban) compared to standard dose in a subpopulation of patients without renal impairment
- To describe the risk of fatal bleedings in patients with NVAF (overall population as well as patients with renal impairment) initiating treatment with reduced dose of individual NOACs (rivaroxaban, apixaban, edoxaban) compared to standard dose in a subpopulation of patients without renal impairment
- To describe the risk of intracranial hemorrhage (ICH) in patients with NVAF (overall population as well as patients with renal impairment) initiating treatment with reduced dose of individual NOACs (rivaroxaban, apixaban, edoxaban) compared to standard dose in a subpopulation of patients without renal impairment

9. **Research methods**

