9.3.4 Subpopulations and Subgroups

Subgroups and subpopulation are only build on the basis of conditions already present at index date.

The following subpopulations of special interest will be defined:

• Patients with renal impairment initiating either phenprocoumon or reduced doses of NOACs

Patients with renal impairment will be identified based on primary and secondary hospital diagnoses or verified ambulatory diagnoses in the baseline period according to Fleet et al. (9) and Nielsen et al. (4) (see definition of renal impairment as covariate in Annex 3: Additional information).

• Patients with chronic renal disease initiating either phenprocoumon or reduced dose of NOACs

Patients with chronic renal disease will be identified based on primary and secondary hospital diagnoses or verified ambulatory diagnoses (ICD 10 GM code N18.3 and N18.4) in the baseline period.

The following subgroups of special interest will be defined. Analyses will be conducted also including a test for effect modification (interaction):

• Frail patients

Frailty can be operationalized in several ways, but is commonly characterized by a set of signs and symptoms in geriatrics and gerontology research. While difficult to assess in administrative claims data, the recently validated claims based Frailty Indicator (10) will be used in this study. This algorithm is

validated using against the frailty phenotype, which is the most widely used instrument for assessing frailty. The frailty cut-off for this study will be 0.25 as the desire is to specifically identify frail individuals.

• Age group (<=79 vs. 80+ years)

Age will be assessed at the index date.

• Renal impairment

Patients with renal impairment will be identified based on primary and secondary hospital diagnoses or verified ambulatory diagnoses in the baseline period according to Fleet et al. (9) and Nielsen et al. (4) (see definition of renal impairment as covariate in Annex 3: Additional information).

• Prior IS or SE

Patients with IS, TIA or SE will be identified based on primary and secondary hospital diagnoses or verified ambulatory diagnoses in the baseline period according the definition for IS/TIA and SE as covariate (see Annex 3: Additional information).

• Reduced vs. standard dose of NOACs

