For each respective NOAC, patients will be classified into reduced and standard dose initiators. Analyses will be conducted comparing reduced dose initiators vs. phenprocoumon and standard dose initiators vs. phenprocoumon.

• Malignant cancer (excl. non-melanoma skin cancer)

Patients with malignant cancer (excl. non-melanoma skin cancer) will be identified based on primary and secondary hospital diagnoses or verified ambulatory diagnoses in the baseline period according the definition for malignant cancer as covariate (see Annex 3: Additional information). For the subgroup of patients with cancer, the different underlying cancer-types will additionally be included as covariates in the respective statistical models.

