9.7.2 Main analysis

Analyses will be conducted in line with good statistical practices. Models will use confounding factors to adjust for group differences. However, unmeasured confounding and resulting confounding bias affecting point estimates, confidence intervals and any p-values in the treatment group comparisons may remain.

In a first step, Cox proportional hazards regression models will be applied in in each treatment group compared to phenprocoumon (reference) to estimate crude and confounder adjusted hazard ratios (HRs) of the above mentioned outcomes as well as treatment discontinuation (persistence) with accompanying 95% confidence intervals and *p*-values. Persistence (risk of non-persistence) will also be calculated separately for specific time points of interest (months 3, 6, 9, 12, 18 and 24). In the analysis of reduced vs. standard dose of NOACs, the standard dose will be used as reference. Kaplan-Meier cumulative incidence plots will be generated to characterize risk of outcome events of interest over time.

Information on confounding factors which are planned to be included in the models as well as in the estimation of the propensity score can be found in section 9.3.3.

In a second step, we will use the stabilized inverse probability of treatment weighting (IPTW) approach based on the propensity score to adjust for potential confounding resulting from imbalances in the baseline characteristics of different treatment groups. The objective of IPTW

based analysis is to create a weighted sample, for which the distribution of possible confounding variables is approximately the same between comparison groups (12,13). The propensity score is defined as the patient's probability to receive a treatment under investigation (i.e. phenprocoumon for main analyses and standard dose for the analyses of reduced vs. standard dose of NOACs) given a set of known patient's baseline characteristics. Propensity scores will be calculated using multiple logistic regression on a relevant set of patient characteristics listed in section 9.3.1 for each 1:1 comparison separately, e.g. rivaroxaban vs. phenprocoumon, rivaroxaban 15 mg vs. rivaroxaban 20 mg etc.

Let Z be an indicator variable relating to the treatment received by a patient, Z = 1 for an active treatment (e.g. rivaroxaban), Z = 0 for a control treatment (warfarin), and let X denote a vector of observed patient baseline characteristics. Then the propensity score is e = P(Z = 1|X). The inverse

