probability of treatment weight is defined as $w = \frac{Z}{e} + \frac{1-Z}{1-e}$, i.e.

$$w = \frac{1}{e}$$
 for patients receiving the active treatment, and $w = \frac{1}{1-e}$ for patients receiving the control treatment.

Weighting by the inverse probability of treatment results in an artificial population or synthetic sample, in which treatment assignment is independent of measured baseline characteristics. Of note, a very low propensity score of subjects receiving an active treatment, or a propensity score close to 1 of subjects receiving a control treatment result in large weights. Such weights increase the variability of the estimated treatment effect (12). Moreover, it is known that the sample size of the synthetic sample is always greater that the sample size of the original data. Consequently, regression estimates with IPTW tend to have smaller confidence intervals because of the inflated sample sizes. In our analysis we will use IPTW with stabilized weights (12,13) which ensure more robust effect estimates. The stabilized weight is defined as $sw = \frac{P(Z=1)*Z}{e} + \frac{(1-P(Z=1))*(1-Z)}{1-e}$. The use of stabilized weights in the synthetic data preserves the sample size of the original data set (12). The application of propensity score methods via stabilized weights requires overlap of the propensity score distribution in the active and control treatment group. Therefore distributions of propensity scores will be inspected for original data and the synthetic sample. Furthermore, the distribution of stabilized weights in the original data will be examined to determine, if large weights remain after stabilization of weights. By applying IPTW method using the propensity score assessment needs to be done, whether weighting procedure succeeded to balance patient characteristics between treatment groups. The distributions of propensity scores and stabilized weights will be inspected for original data and the synthetic sample. The balance of patient characteristics between treatment groups will be checked by using standardized mean differences (SMD). An absolute SMD of 0.1 or less will be considered as a negligible difference between groups. For continuous variables, the SMD is calculated via

$$SMD_{cont} = \frac{\overline{X_T} - \overline{X_C}}{\sqrt{\frac{S_T^2 + S_C^2}{2}}},$$

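### The four dose-comparison objectives in section 8.3 contradict themselves on renal status, and no other section says which population both dose arms come from

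*Protocol*

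**What the plan says.** Section 8.3 has four bullets, one each for IS/SE, severe IS, fatal bleeding and ICH. All four describe the patients as "overall population as well as patients with renal impairment) initiating treatment with reduced dose of individual NOACs" and close with "compared to standard dose in a subpopulation of patients without renal impairment".

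The cover table and abstract keep the same ending. In place of renal impairment they refer only to unnamed subpopulations of interest. They also merge the four outcomes into one line: "To describe the risk of IS/ SE, severe IS, fatal bleeding and ICH as combined effectiveness outcome in patients with NVAF".

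The methods sections bear on the comparison as follows:

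- Section 9.3.4 defines a renal subpopulation as "Patients with renal impairment initiating either phenprocoumon or reduced doses of NOACs", which has no standard-dose arm. For the dose subgroup it says "Analyses will be conducted comparing reduced dose initiators vs. phenprocoumon and standard dose initiators vs. phenprocoumon".
- Section 9.7.2 plans a direct dose contrast: "In the analysis of reduced vs. standard dose of NOACs, the standard dose will be used as reference". Propensity scores are estimated "for each 1:1 comparison separately, e.g. rivaroxaban vs. phenprocoumon, rivaroxaban 15 mg vs. rivaroxaban 20 mg etc". It assigns Cox regression, IPTW and matching to this comparison and notes that weighting "requires overlap of the propensity score distribution in the active and control treatment group".

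**The concern.** A dose comparison needs one population from which both arms are drawn. Section 8.3 gives two that exclude each other, so whoever programs the analysis must decide which half of each sentence to override. One possible choice draws the two arms from different renal strata.

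That matters for this question in particular. Section 7 motivates it with the worry that off-label dose reduction may make these drugs less effective. A reduced-dose arm enriched with kidney disease, set against a standard-dose arm with none, could show a higher event rate without any effect of dose. Choosing the population after the data have been seen would be post hoc.

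**Working it through.** The protocol gives no figure for this comparison: Table 3 is not split by dose or renal status. The check is therefore mainly one of logic, with an illustration of size.

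**1. The two literal readings of 8.3.**

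- *Restriction on both arms.* Patients who are impaired and also not impaired form an empty set, so the renal-impairment result contains 0 patients. The overall result becomes a result in unimpaired patients only.
- *Restriction on the standard-dose arm only.* Within the analysis set, the probability of standard dose given renal impairment is 0 by construction. Impaired reduced-dose patients have no counterpart, so positivity fails for them. Unimpaired reduced-dose patients still overlap with the reference arm.

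**2. Whether another section decides.** Section 9.3.4 compares each dose with phenprocoumon, not dose with dose. It also lists renal impairment as a subgroup factor with an interaction test. That implies a complementary group without impairment, but the group is not tied to the dose comparison. Sections 9.3.1 and 9.7.2 describe the dose-against-dose contrast with no renal restriction. The question stays open.

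**3. Whether adjustment would repair the second reading.** Section 9.7.2 takes its confounders from the list in 9.3.3. That list does not name renal impairment. It enters only through the modified HAS-BLED score, where Annex 3 merges liver and renal disease into one item. Annex 3 does define renal impairment under its covariate heading, so inclusion may be intended, but the list does not say so. If it is left out, the models would run without visible failure and the dose hazard ratio would absorb part of the renal effect.

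**4. Illustrative size under the second reading.** Let p be the share of reduced-dose initiators with renal impairment and R the event-rate ratio, impaired to unimpaired. With no true dose effect and no impaired patients in the standard-dose arm, the crude ratio is

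1 + p(R − 1).

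The protocol gives neither p nor R for this population. I assume p from 0.3 to 1.0, where 1.0 is the renal-impairment version of the objective. For R the protocol offers only a rough anchor: section 7, Figure 1 has 3.40 ischemic strokes per 100 person-years on rivaroxaban 15 mg with renal impairment, and Table 3 assumes 2.2 IS/SE per 100 person-years for all rivaroxaban users. So 3.40/2.2 = 1.55.

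| p | R = 1.2 | R = 1.55 |
|---|---|---|
| 0.3 | 1 + 0.3 × 0.2 = 1.06 | 1 + 0.3 × 0.55 = 1.165 |
| 0.5 | 1 + 0.5 × 0.2 = 1.10 | 1 + 0.5 × 0.55 = 1.275 |
| 1.0 | 1 + 1.0 × 0.2 = 1.20 | 1 + 1.0 × 0.55 = 1.55 |

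The anchor is weak. It sets impaired patients against all users rather than unimpaired ones, and it sets IS against IS/SE. The same two sources give other ratios: 0.78/0.5 = 1.56 (ICH, rivaroxaban), 3.39/2.5 = 1.36 and 2.46/2.5 = 0.98 (stroke, phenprocoumon, under two exposure definitions), 0.99/0.7 = 1.41 and 0.86/0.7 = 1.23 (ICH, phenprocoumon). At R = 0.98 there would be practically no bias.

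**The case against.** The strongest reply is that a sensible reading exists and can be run: reduced against standard dose, with both arms free of renal impairment. The parenthesis in 8.3 matches the one used throughout the later bullets of 8.2 and looks carried over. The cover table and abstract name no renally impaired group in this objective. The rationale concerns off-label reduction, and 9.7.2 describes a plain within-drug contrast. This may well be what was meant, and it rules out saying that the comparison cannot be run at all. But 8.3 does not say it, and neither 9.3.4 nor 9.7.2 restricts the analysis set accordingly.

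A reader might also infer stronger faults that the text does not support:

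- *That the weights would be undefined.* Under the formula in 9.7.2, a treated patient with score 1 gets 1/1 = 1 and a control with score 0 gets 1/(1 − 0) = 1. The weights exist but balance nothing. Scores of exactly 0 or 1 would also require renal impairment in the model, and 9.3.3 does not list it.
- *That there is no overlap anywhere.* In the overall version, unimpaired patients overlap. If renal impairment were in the adjusted Cox model, they would still identify the dose effect.
- *That the final hazard ratio would be off by a known amount.* The ratios shown are crude and rest on assumed inputs. Values of R near 2 have no support in the protocol.
- *That a stroke-plus-bleeding composite is planned.* Sections 8.3, 9.3.2 and 9.7.1 treat the outcomes separately. The abstract line is a loose summary.

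Finally, these are third-tier descriptive objectives, and the abstract says that p-values and intervals are not confirmatory. That lowers the stakes but does not supply a population.

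**Conclusion.** The point holds as a contradiction in the stated population of all four objectives in 8.3, left open by the rest of the protocol. It depends on no assumption. The consequence does depend on the reading. With the restriction on both arms, the renal-impairment result is empty and the overall label is wrong. With it on the standard-dose arm only, positivity fails for impaired reduced-dose users and the dose estimate is open to confounding by kidney disease, the more so because 9.3.3 omits renal impairment apart from the combined HAS-BLED item. The crude distortion in that case would be 1.06 to 1.55 for p from 0.3 to 1.0 and R from 1.2 to 1.55, all assumed. The primary and secondary comparisons with phenprocoumon are not touched. Which dose suits which patient is not at issue here.

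**What to change.** - In 8.3, state one renal stratum that applies to both dose arms. One option is reduced against standard dose among patients without renal impairment by the Annex 3 definition, with the parenthesis deleted from all four bullets.
- If a dose comparison in renally impaired patients is wanted, list it as a separate objective with both arms impaired.
- Carry the chosen population into the cover table, the abstract, 9.3.4 (as a defined subpopulation for the dose comparison) and 9.7.2 (as the analysis set for that comparison).
- As a minor alignment, reword the cover table and abstract so that only IS/SE is called combined, as in 8.3, and the other three outcomes stand separately.

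The cost is wording in five places. No new data are needed, and it should be done before the dose analyses are run.

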9.1 Study design

We will conduct a non-interventional retrospective cohort study based on German claims data from the InGef (Institute for Applied Healthcare Research Berlin) research database between January 2012 and December 2017. Data from 2012 will only be used for the assessment of demographic and clinical characteristics and to identify new users of NOACs and phenprocoumon. The enrollment period will be from 01 January 2013 to 30 June 2017. Data from 1 July to 31 December 2017 will considered as follow-up only to allow a follow-up of at least 6 months.

9.2 Setting

9.2.1 Study population and selection criteria

The source population of this study will include all insured members of approximately 64 German statutory health insurances (SHIs) contributing data to the InGef database.

9.2.2 Inclusion criteria

Patients must meet all of the following inclusion criteria (see Annex 3: Additional information for detailed operationalization) to be eligible for the study (a detailed definition:

- Patients with a first NOAC (rivaroxaban, apixaban, edoxaban) or phenprocoumon prescription (index drug) in the enrollment period between 1st January 2013 to 30th June 2017 (index date), i.e. without prior prescription of any NOAC or phenprocoumon in the 12 months before the first prescription in the enrollment period;
- Age of at least 18 years at index date;
- Continuous enrollment in the 12 months before the first NOAC (rivaroxaban, apixaban, edoxaban) or phenprocoumon prescription in the enrollment period (baseline period);
- A verified ambulatory or primary/ secondary hospital discharge diagnosis of NVAF in the 12 months before the first NOAC (rivaroxaban, apixaban, edoxaban) or phenprocoumon prescription in the enrollment period (baseline period);

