 - o Erythropoietin-simulating agents
 - o Estrogens
 - o Lipid modifying agents
 - Non-steroidal anti-inflammatory drugs
 - o Proton-pump inhibitors
- Other indicators of overall health status

- Number of hospitalizations
- Number of different medications used (based on 7 digit ATC codes)
- o Number of ambulatory physician visits

Others

- Year of cohort entry
- Duration of follow-up in days
- Type of cohort exit (end of study period, switch, discontinuation, death, etc.)

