9.5 Study size

Based on previous studies, we estimate a sample size of approximately 90,000 new users of oral anticoagulants (16,800 apixaban, 6,800 dabigatran, 1,600 edoxaban, 30,200 rivaroxaban and 35,400 phenprocoumon) with NVAF between 1st January 2013 to 30th June 2017. We used the event rates from a previous study based on the InGef research database (6) to estimate the expected number of ICH and IS/SE as primary study outcomes and the precision of the estimated expected events in users of all study drugs assuming an average follow-up time of 1 year per person. As edoxaban was not included in this study, we assumed the lowest event rate obtained for all NOACs to obtain conservative estimates

Table 3 Expected number of primary outcome events and corresponding precision assuming an						
average follow-up of one year per patient						

Overall		Intracranial hemorrhage			Ischemic stroke/systemic embolism			sm	
Oral anticoagulant	Estimated number of drug users	Estimated incidence rate	Expected events	Lower 95%- CI	Upper 95%- CI	Estimated incidence rate	Expected number of events	Lower 95%- CI	Upper 95%- CI
Phenprocoumon	35,400	0.007	248	218	279	0.025	885	828	944
Apixaban	16,800	0.004	67	52	84	0.027	454	413	496
Rivaroxaban	30,200	0.005	151	128	176	0.022	664	614	715
Edoxaban	1,600	0.004	6	2	12	0.022	35	24	48

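### One enrolment window serves all drugs with no concurrent-comparator rule, so if edoxaban entered late, its crude, Kaplan-Meier and IPTW contrasts rest partly on historical phenprocoumon controls

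*Protocol*

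**What the plan says.** - **Window.** Section 9.1: "The enrollment period will be from 01 January 2013 to 30 June 2017". Section 9.2.2 applies the same dates to every index drug: a first NOAC "or phenprocoumon prescription (index drug) in the enrollment period between 1st January 2013 to 30th June 2017". No drug has its own start date, and no rule ties phenprocoumon starters to the period of use of the NOAC they are compared with.
- **Expected users.** Section 9.5: "16,800 apixaban, 6,800 dabigatran, 1,600 edoxaban, 30,200 rivaroxaban and 35,400 phenprocoumon". The event rates come from an earlier study of the InGef database: "As edoxaban was not included in this study, we assumed the lowest event rate obtained for all NOACs". Section 7 presents that study as covering all NOACs, but the agents it reports are apixaban, dabigatran and rivaroxaban.
- **Overlap.** Section 9.7.2 says that stabilised weighting "requires overlap of the propensity score distribution in the active and control treatment group". Score and weight distributions are then inspected, and an absolute SMD of 0.1 or less counts as negligible. No restriction follows if overlap fails.
- **Calendar time.** "Year of cohort entry" is listed in Section 9.3.3 under other variables, next to duration of follow-up and type of cohort exit, which arise after the index date. Section 9.7.2 first sends the reader to 9.3.3 for the confounders in the models and the propensity score. It then sends the reader to 9.3.1, the exposure definition, for the propensity variables. Section 9.9 does not list calendar time as a limitation.

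**The concern.** Edoxaban against phenprocoumon is one of three pairwise contrasts for each primary outcome (IS/SE and ICH). If edoxaban first appears in the data some way into the 54-month window, phenprocoumon patients who started before then could not have received it in this database. They still count in full in the comparator group.

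Any change over calendar time in event rates, coding, or the kind of patient who still starts phenprocoumon would then be read as a drug effect. Section 7 says NOAC use is increasing, so a change in who starts phenprocoumon is plausible, although the protocol documents no trend in event rates.

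Eligibility and choice of comparator are matters for the protocol, so this is not a detail to leave to the SAP.

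**Working it through.** **1. The plan's own figures.** Section 9.5 multiplies users by rate, "assuming an average follow-up time of 1 year per person".
- Edoxaban: 1,600 × 0.022 = 35.2 IS/SE (stated 35); 1,600 × 0.004 = 6.4 ICH (stated 6).
- Phenprocoumon: 35,400 × 0.025 = 885 IS/SE (stated 885); 35,400 × 0.007 = 247.8 ICH (stated 248).

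These reproduce. They refer to the overall population. The protocol gives no counts for patients with renal impairment.

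**2. Assumptions.** No entry date is given for any NOAC. I assume even phenprocoumon accrual over the 54 months and no edoxaban for the first m months, with m = 12, 24 or 30. At m = 0 every effect below is zero.

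**3. Non-concurrent share** = m/54, and count = 35,400 × m/54.
- m = 12: 22%, 7,867 starters before entry, 27,533 after
- m = 24: 44%, 15,733 before, 19,667 after
- m = 30: 56%, 19,667 before, 15,733 after

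**4. What stabilised weighting does.** Let e be the probability of edoxaban, and let the score separate pre-entry from post-entry time. Pre-entry phenprocoumon patients have e = 0, so their stabilised weight is 1 − P(Z=1) = 35,400/37,000 = 0.96. They stay in almost unchanged. Post-entry controls have e = 1,600/(1,600 + Npost), so apart from the common factor 0.96 their weights sum to Npost/(1 − e) = Npost + 1,600. The weighted pre-entry prevalence among controls is therefore

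p = Npre/(Npre + Npost + 1,600) = Npre/37,000 = 0.213, 0.425, 0.532.

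Among edoxaban users it is 0, because no such patient exists to be weighted up.

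**5. SMD** = p/√(p(1 − p)/2) = 0.73, 1.22, 1.51. (The binary formula in Section 9.7.2 carries a factor of 100, left out here to match the 0.1 limit.) The limit is reached when 2p/(1 − p) = 0.01, i.e. p = 0.005, or about 184 pre-entry starters: 184/35,400 × 54 months is roughly 9 days. This concerns the pre-entry flag. Failure on calendar year itself needs a full year without edoxaban.

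**6. What that could do to a hazard ratio (illustration only).** Suppose the event rate changes by a factor g per year of entry and the true HR is 1. The mean relative rate over years a to b is (g^a − g^b)/(−ln g × (b − a)). For m = 24 and g = 0.9, this is 0.902 for years 0 to 2 and 0.712 for years 2 to 4.5. The IPTW HR is about 0.712/(0.425 × 0.902 + 0.575 × 0.712) = 0.90. With g = 1, 0.95 or 0.8 it is 1.00, 0.95 or 0.79. The protocol supplies no g.

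**7. Precision after restriction.** The unadjusted 95% CI factor is exp(1.96 × √(1/d1 + 1/d0)).
- IS/SE, all starters: d1 = 35.2, d0 = 885, factor 1.40. For m = 12, 24, 30: d0 = 688, 492, 393, factors 1.40, 1.41, 1.41. With only 12 concurrent months: d0 = 197, factor 1.43.
- ICH: 2.19 with all starters (6.4 and 247.8 events), 2.27 with only 12 concurrent months (6.4 and 55).

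**The case against.** **The premise is inferred.** No entry date is given. Slow uptake, or the period or design of the earlier study, could also explain 1,600 users and edoxaban's absence from it. This stands, and the point is therefore conditional.

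**Not every NOAC is affected.** A reader might infer that rivaroxaban and apixaban are compared with historical controls too. The documents do not support that. Nothing shows a time in 2013 to 2017 when either could not be started, and the look-back ("Data from 2012 will only be used for the assessment of demographic and clinical characteristics and to identify new users of NOACs and phenprocoumon") presumes some NOAC use before the window, without naming a drug.

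**Not every method fails.** A reader might also infer that listing year of entry is useless throughout. That goes too far. In a Cox model with year as a categorical term, the drug effect is estimated from years in which both drugs occur, and earlier phenprocoumon starters mainly inform the year terms. In 1:1 nearest-neighbour matching with year in the score, planned for both primary outcomes, pre-entry controls have scores near zero and would mostly go unmatched. Both analyses are largely protected, provided year is really used. The conflicting pointers to 9.3.3 and 9.3.1 leave that unsettled.

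**Diagnostics exist.** An SMD of 0.7 or more would be noticed, and the response might be placed in the SAP. Noticing it does not repair an eligibility rule, however, and choosing the window after seeing the data is worse than fixing it beforehand.

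**The size is for the wrong population.** The counts are for all NVAF patients, whereas the primary objective concerns renal impairment. This is fair. The percentages carry over only if accrual is similar there, and the counts do not carry over.

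**Longer possible follow-up of 2013 starters** adds little: follow-up is on treatment, and Cox regression handles unequal administrative censoring.

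**Conclusion.** The point holds in a limited, conditional form. The protocol sets one window for all drugs and has no concurrent-comparator rule. Its own figures make late entry of edoxaban a fair inference, not a fact. If edoxaban entered late, the crude Cox, Kaplan-Meier and IPTW edoxaban contrasts mix concurrent and historical phenprocoumon controls, and no propensity score can rebalance the IPTW analysis.

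Under even accrual and 12 to 30 months without edoxaban, 22% to 56% of phenprocoumon starters in the overall population are non-concurrent, with an SMD of about 0.7 to 1.5 against 0.1. The resulting bias in the hazard ratio depends on a calendar trend that the documents do not give, and without such a trend it is nil. Adjusted Cox and matching are largely safe if year of entry is in them, which Section 9.7.2 does not firmly fix.

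**What to change.** Add to Section 9.2.2: for edoxaban, and for any other NOAC first dispensed after 1 January 2013, both groups in that pairwise comparison are restricted to index dates on or after the first eligible dispensing of that NOAC in the InGef data.

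In Section 9.7.2, estimate the propensity score within that window, include calendar period of entry as a categorical term in both the score and the Cox model, and correct the reference for the propensity variables from 9.3.1 to 9.3.3, leaving out the post-index items listed there.

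The cost is some wording and one date filter per comparison. The rule takes its date from the data, so no outside launch date is needed. The downside is fewer phenprocoumon comparators for edoxaban: 27,533, 19,667 or 15,733 would remain in the overall population under the three assumed dates. Precision hardly changes, because edoxaban's own events (about 35 IS/SE and 6 ICH) dominate the variance. If a NOAC was dispensed from the first day, the filter removes nobody.
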